6.2 FIDELITY

PA Coach will be trained by [name] and will conduct mock sessions of all OA-PCP calls prior to study initiation.

6.3 MEASURES TO MINIMIZE BIAS: RANDOMIZATION AND BLINDING

N/A – This is a single group, pre-post pilot trial of the OA-PCP.

6.4 STUDY INTERVENTION ADHERENCE

The study database will be used to track participants' completion of all assessment visits, as well as all intervention contacts. The coordinator will also maintain close communication with the PA coach regarding

intervention delivery. If participants miss intervention calls, a study team member may assist the PA coach in attempting to reach the participant.

6.5 CONCOMITANT THERAPY

Participants will be permitted to continue any other OA treatment during the course of the study.

7 STUDY INTERVENTION/ DISCONTINUATION AND PARTICIPANT DISCONTINUATION/WITHDRAWAL

7.1 DISCONTINUATION OF STUDY INTERVENTION

When a participant discontinues from the OA-PCP intervention but not the study, remaining study procedures (e.g., follow-up assessments) will be completed as indicated by the study protocol. If a clinically significant finding is identified after enrollment (e.g. health-related changes that may change the safety level of participating in an independent PA program), the investigator or qualified designee will determine if any change in participant management is needed. Any new clinically relevant finding will be reported as an adverse event (AE). The data to be collected at the time of study intervention discontinuation will include the reason(s) for discontinuing the participant from the intervention, and methods for determining the need to discontinue.

7.2 PARTICIPANT DISCONTINUATION/WITHDRAWAL FROM THE STUDY

Participants are free to withdraw from participation in the study at any time upon request. An investigator may discontinue a participant from the study for the following reasons:

- Lost-to-follow up; unable to contact subject
- Any event or medical condition or situation occurs such that continued collection of follow-up study data would not be in the best interest of the participant or might require an additional treatment that would confound the interpretation of the study
- The participant meets an exclusion criterion (either newly developed or not previously recognized) that precludes further study participation

The reason for participant discontinuation or withdrawal from the study will be recorded in the study database. Participants who discontinue or are withdrawn will be replaced up to the point of randomization assignment being given to the participant. Once participants are given their randomization assignment, they will be counted toward the total study sample size and not replaced.

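### Section 7.2 lets an investigator end a participant's follow-up because a treatment might confound interpretation, which fits poorly with the intent-to-treat approach in Section 9.3

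*Combined protocol and SAP*

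**What the plan says.** Section 7.2 introduces its list with "An investigator may discontinue a participant from the study for the following reasons". The second item joins two grounds with an 'or'. One is that further follow-up would not serve the participant. The other is that an event "might require an additional treatment that would confound the interpretation of the study". The third item is "The participant meets an exclusion criterion (either newly developed or not previously recognized) that precludes further study participation". The section adds that "The reason for participant discontinuation or withdrawal from the study will be recorded in the study database".

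Section 7.1 covers the lesser step: "When a participant discontinues from the OA-PCP intervention but not the study, remaining study procedures (e.g., follow-up assessments) will be completed". Section 6.5 says "Participants will be permitted to continue any other OA treatment during the course of the study". It does not mention newly started treatment, and no section says which treatments would count as confounding.

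On analysis, Section 9.3 names an intent-to-treat approach for the primary analyses without defining it. Section 9.4 plans paired t-tests of MVPA and the secondary outcomes and gives no method for missing values. Section 8.1 sets outcome collection at baseline and 4 months. Section 6.3 describes the design: "This is a single group, pre-post pilot trial of the OA-PCP".

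**The concern.** Withdrawal at the participant's request, or in the participant's interest, is unavoidable. This ground is different. The plan itself authorises giving up an outcome because the outcome might be hard to interpret. The wording needs only that a treatment might be required; none need have started.

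Events that call for additional treatment in people with osteoarthritis could plausibly go with changes in activity, pain or function, which are the study's outcomes. If so, the participants left in the paired analysis are selected on something related to the result. With no control group, no comparison would reveal the selection. At stake are the mean pre-post change in MVPA and WOMAC and, to a lesser degree, the follow-up completion proportion that Section 8.1 intends to use in planning a larger trial.

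**Working it through.** No figure in the plan is in dispute. Section 9.2 sets the sample size on feasibility, with no effect size, SD or power to reproduce. The check is a reading of the sections against each other, then an illustration of size.

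**Reading**

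1. Section 7.2 concerns leaving the study, not only the intervention. Section 7.1 continues assessments only for those still in the study. Using the ground therefore ends outcome collection.
2. Section 8.1 gives one follow-up time point, 4 months. A participant removed earlier has no other follow-up value to fall back on.
3. The sentence in 7.2 is loosely built. On its natural reading, the event is what might require the treatment. The participant-interest ground stands separately before the 'or', so the second ground adds something that participant interest does not cover.
4. An intent-to-treat approach ordinarily keeps people in view whatever happens after entry. The ground permits the opposite for one class of post-enrolment event.
5. A paired t-test needs both values, so a removed participant contributes nothing to it.

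**Size, illustration only**

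Inputs from the documents: N = 60 (Section 4.1); retention of about 90% (Section 9.4), so 0.90 × 60 = 54 pairs; 52 participants with valid follow-up accelerometer data (Section 8.1), so at most 52 pairs if that count is from this cohort.

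Assumed inputs, with no support in the documents: the number removed under this ground, k = 1 to 3; and the difference in mean change between those kept and those removed, D = 0.5 to 1.0 SD of the change.

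The mean of all 60 is a weighted average of those kept and those removed, so the shift from analysing only those kept is (k/60) × D:

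- k = 1, D = 0.5: 0.5/60 = 0.008 SD
- k = 1, D = 1.0: 1.0/60 = 0.017 SD
- k = 3, D = 0.5: 1.5/60 = 0.025 SD
- k = 3, D = 1.0: 3.0/60 = 0.05 SD

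For scale, the half-width of a 95% confidence interval for the mean change, in SDs of the change, is t(0.975, n−1)/√n. This is 0.273 for n = 54 and 0.278 for n = 52. Against 0.273, the smallest shift is 0.0083/0.273 = 3% and the largest is 0.05/0.273 = 18%. The sign depends on whether those removed would have done worse or better than those kept, which is not known.

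**The case against.** The strongest objection is that intent-to-treat is undefined here and there is no randomised assignment. The next sentence of Section 9.3 contrasts it with samples that completed more of the intervention contacts, so it may mean only that people are analysed regardless of adherence. On that view 9.3 governs the analysis set, 7.2 governs data collection, and a removed participant stays in the set with a missing value. This stands in part: the mismatch is a poor fit, not a formal contradiction. But a participant with no 4-month value still drops out of the paired t-test. Any missing value has that effect; this loss differs in being one the plan chooses to permit.

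The practical weight is also limited. The ground is optional. Section 9.1 calls the study exploratory with no hypothesis testing, although Section 9.4 plans tests at the 0.05 level. The inputs to the size illustration are assumed. All of this lowers the importance without removing the point.

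Four stronger readings are tempting, and the documents do not support them:

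- A reader might infer that Sections 7.1 and 7.2 contradict each other, or leave it open which governs a health change. Their scopes differ: 7.1 deals with leaving the intervention and 7.2 with leaving the study. Section 7.1 leaves the response to a clinically significant finding to the investigator or a designee. That discretion is a design choice.
- A reader might infer that the exclusion-criterion ground has the same fault. It is permissive and limited to criteria that preclude further participation, and it does not turn on confounding.
- A reader might infer that the result will look too favourable. Nothing in the documents fixes the direction or says how often the ground would be used.
- A reader might infer that each removal lowers measured retention. That holds only if the participant would otherwise have completed. Section 7.3 suggests removals count as losses. The replacement rule, "Once participants are given their randomization assignment, they will be counted toward the total study sample size and not replaced", has no clear meaning in a single-group study, but that is a separate matter.

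**Conclusion.** The point holds in a limited form. Section 7.2 permits follow-up to end for an analytic reason tied to a post-enrolment event. This fits poorly with the approach named in Section 9.3 and feeds directly into the pairs-only analysis in Section 9.4. It is a minor point, worth correcting because the correction is cheap.

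The effect is probably small: 0.008 to 0.05 SD if 1 to 3 of 60 are removed and their change differs by 0.5 to 1.0 SD. Both inputs are assumptions, and the sign is unknown. The conclusion about the wording does not depend on them.

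Timing is uncertain. Section 8.1 reports in the past tense valid accelerometer data for 57 participants at baseline and 52 at follow-up. Since 57/60 = 95% and 52/60 = 86.7%, against the stated 95% and 86%, these counts fit a cohort of 60. If they are this trial's data, collection is finished and only the reporting can change. The documents do not settle that.

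**What to change.** In Section 7.2, delete the words "might require an additional treatment that would confound the interpretation of the study", with the 'or' before them, as a ground for ending data collection. Leave the best-interest and exclusion-criterion grounds unchanged. State that the 4-month phone and accelerometer assessments are collected regardless of additional treatment. The change concerns data collection only; all treatment and intervention decisions remain with clinical judgement.

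If follow-up is already complete, report participants removed by an investigator separately from those who could not be contacted. Section 7.2 already requires the reasons to be recorded, so no new data are needed.

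The cost is one deleted clause, one added statement and a few more remote assessments of a kind already planned for every participant. The downside is that some outcomes will be measured after additional treatment, so the mean change will include whatever that treatment contributed, and the report should say so.

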7.3 LOST TO FOLLOW-UP

A participant will be considered lost to follow-up if he or she fails to complete the 4-month follow-up assessment. If a participant misses intervention calls prior to the 4-month time point and cannot be contacted during the time frame, the study team will still attempt to contact the participant for remaining calls / assessments. The study team must attempt to contact a participant at least 3 times, on different days of the week, different times of day, and across at least 2 weeks, before they are considered to have missed a visit / assessment or be lost to follow-up. These contact attempts will be documented in the study database.

8 STUDY ASSESSMENTS AND PROCEDURES

8.1 ENDPOINT AND OTHER NON-SAFETY ASSESSMENTS

Measures will be collected at baseline and 4-months by a trained research assistant. Other than the accelerometer, measures will be administered via phone. Participants will be paid \$25 for completing each phone-based measure and \$15 for returning the accelerometer device at each time point.

Primary Efficacy Outcome: Objectively Assessed Physical Activity.

We selected this as the primary study outcome because PA is the target of the intervention, and objective assessment has advantages over self-report in terms of accuracy ⁷². Our specific primary outcome of interest is minutes of moderate to vigorous intensity PA (MVPA) per week, since this corresponds to DHHS recommendations and is a known predictor of outcomes in patients with OA ⁷³. We will also examine step counts, minutes of sedentary activity and other complementary metrics, as these are also important for providing a broad picture of PA among participants ^{74,75}. Each participant will be asked to wear the Actigraph GT3X+ (Pensacola, FL), which allows for the collection and manipulation of raw actigraphy data to facilitate accurate assessment of PA ⁷⁶. Participants will be asked to wear the monitors during all waking hours for 7 days. Following previously established thresholds, outcomes will only be computed for participants who wear the accelerometer for 4+ days with 10+ hours of daytime wear. Monitors will be worn on the waist, using either an elastic belt or clip, over the right hip. We may ask a subset of participants to wear a wrist-worn monitor in addition to the waist-worn monitor, in order to assess acceptability and compare values obtained from monitors worn at the two different sites. Accelerometers will be mailed with instructions and a pre-stamped / addressed return envelope. Several days after the accelerometer has been mailed, a study team member will call the participant to review instructions. A phone number will be provided for problems or questions. A second call will be made toward the end of the 7 days to ask about wear and to remind participants to return the monitor. If participants have not worn the monitor enough, they will be asked to wear the monitor a few extra days. Drs. [name], [name] and [name] have been involved with projects that have successfully mailed accelerometers to and / or from study participants with OA. There have been high rates of adherence (4+ days with 10+ hours of wear); 93% in one study of adults and partners with OA and 89% in another of 140 patients with OA, with minimal loss of monitors (< 2%). In Aim 2 of this project, valid accelerometer data were available for 57 participants at baseline (95%) and 52 participants at follow-up (86%). Upon return, accelerometer data will be downloaded, compiled into 60s epochs, processed to identify wear, non-wear, and sleep periods using current algorithms ^{77,78}, and summarized using cut-points developed by Troiano ⁷⁷ and Mathews ⁷⁹. These cut-points will allow us to calculate minutes of MVPA, as well as sedentary time and step counts.

Secondary Efficacy Outcomes:

Self-Reported Physical Function. Physical function is a key outcome in OA and can be improved with regular PA ^{14,15}. We will assess physical function with the widely used Western Ontario and McMaster Universities Osteoarthritis Index (WOMAC) subscale ^{80,81}; it includes 17 items, rated on a Likert scale of 0 (no difficulty) to 4 (extreme difficulty), that assess difficulty with performing a range of daily activities commonly affected by lower extremity OA. The reliability and validity of the WOMAC total score and subscales have been confirmed ⁸¹. In patients with hip or knee OA, Bellamy et al. reported internal consistency coefficients (Cronbach's alpha) between 0.86 and 0.95 on WOMAC subscales.

Pain (WOMAC). We will assess self-reported pain using the WOMAC subscale ^{14,15}; it includes 5 items, rated on a Likert scale of 0 (no pain) to 4 (extreme pain), that assess pain during a range of daily activities.

Exploratory Outcomes:

Stanford Numeric Rating Scale (NRS) for Fatigue: We will assess self-reported fatigue using the Stanford NRS Scale for Fatigue; it includes 1 item, rated on a Likert scale of 0 (no fatigue) to 10 (severe fatigue), that assesses fatigue in the past 2 weeks.

PROMIS Sleep Disturbance Short Form 4a: We will assess self-reported sleep quality, sleep depth and restoration associated with sleep using the PROMIS Sleep Disturbance instrument; it includes 4 items, with 5 response options ranging in value from 1 to 5.

International Physical Activity Questionnaire (IPAQ): We will assess self-reported physical activity in the last 7

days using the IPAQ(93); it includes 7 items, assessing PA in four life domains: job-related work done outside the home, recreation, transportation and house and yard work.

Participant Characteristics:

We will collect the following information to characterize the study sample: age, race / ethnicity, gender, education, works status, marital status, body mass index, comorbid illnesses ⁸², joints with arthritis symptoms, and duration of knee / hip OA symptoms.

Feasibility and Acceptability:

The following metrics will inform *feasibility* of a larger trial, as well as decisions regarding the number of clinics needed to meet recruitment goals and expected rates of retention:

- Proportion of screened patients who meet the PA eligibility criterion (<150 min per week)
- Proportion of screened patients who are eligible overall
- Proportion of patients who consent to participate, along with refusal reasons for those who do not
- Proportion of participants who complete each phase of the intervention and follow-up assessments

We have developed open-ended questions to assess *acceptability* of the intervention. Topics include acceptability of each intervention component, usefulness of options provided for PA programs / resources, and suggestions for increasing the patient-centeredness of the intervention.

8.2 SAFETY ASSESSMENTS

The study PA coach will be trained to deliver the interventions in adherence to and within the scope of the intervention. If a study team member learns of any adverse events (AEs) that occur in the course of participants' home exercise, this will be documented on the Adverse Events form, as described below.

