1.2 SCHEMA

1.3 SCHEDULE OF ACTIVITIES

	Pre-screening (Pre-consent)	Visit 1 Day 1 to 10	Visit 2 Day 11 to 25	Visit 3 (3 weeks after Visit 2)	Visit 4 (2 weeks after Visit 3)	Follow-up emails at 3 separate time points	Visit 5 (3 months after Visit 3)	Visit 6 (4 months after Visit 3)
EMR Review Eligibility	X							
Screening Phone Call	X							
Informed Consent & HIPAA		X						
Outcome Measures								
Objectively Assessed Physical Activity (accelerometer)			X				X	
Patient Reported Measures:								
-Physical Function (WOMAC)			X					X
-Pain (WOMAC)			X					X
Participant Characteristics			X					
Acceptability								X
OA-PCP Intervention				X	X	X	X	X
Adverse Event Reporting		X	X	X	X	X	X	X

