Motivational interviewing (MI) principles will be used throughout the phone call and will be a particular emphasis for individuals in the pre-contemplation and contemplation stages. These principles are woven into our phone scripts. MI is a key behavior change strategy that can elicit participants' own motivations and / or ambivalence toward PA⁷¹. This helps individuals to explore and resolve their own, sometimes conflicting attitudes toward changing PA behaviors, building autonomy and internal awareness that is essential for long-term behavior change. To support topics discussed during the first phone call, participants will be mailed and / or emailed materials including: 1) handouts describing appropriate exercise for people with osteoarthritis, tips on PA for people with arthritis (including pain management), instructions for different types of exercise (aerobic, strengthening, stretching), and example exercises. 2) A list of PA programs and resources adapted for their locality. 3) A worksheet for documenting PA goals.

Approximately two weeks after the initial call, the PA counselor will contact participants to check in on whether they have successfully connected with PA programs or resources discussed, as well as review progress toward PA goals and set new goals. Content for this call will be tailored based on the first call. The PA counselor will be able to refer to notes from the prior call regarding initial PA goals. If participants have encountered any barriers since the first call, they will be addressed and other PA resources identified if needed. If participants were not ready to set a PA goal or identify PA resources of interest at the first call, they will be invited to do so at call #2.

5. Follow-up emails: At the first call, the counselor will ask participants to opt-in (or opt-out) to receive follow-up emails after the 2-week check in call. For those participants that agree to opt-in, the counselor will email the participant at three separate time points (approximately every 3 weeks) prior to the 3-month follow-up call. The content of the emails will be based on individual PA goals set during previous check in calls.

Phase 3: Linkage to PA Programs and Resources

There are a large number of OA-appropriate, evidence-based PA resources, and a collection of these resources has been developed (and is updated on an ongoing basis) by the OAAA at UNC; a key source for informing this collection is the

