CDC's Compendium of Arthritis Appropriate Physical Activity and Self-Management Education Interventions. Table 2 shows representative examples of these resources, which include tools to facilitate individual PA, as well as group-based classes. With regard to the latter,

we will perform an environmental scan for programs available within the communities surrounding study clinics; this will be facilitated by the OAAA, the Arthritis Foundation's Online Resource Finder and the Evidence-Based Leadership Council. Based on our prior experience, there are many free, appropriate PA programs available in communities, including walking groups and classes in senior centers. Local resource information will be used to tailor patient handouts. Participants will be able to contact the PA counselor throughout the intervention period if they have questions about PA resources, or if they would like information on different resources. We will document the frequency and nature of the contacts to inform and refine the intervention.

Phase 4: PA Counseling Follow-Up

The PA counselor will call participants approximately three months following the initial call, again using our developed phone scripts and tailored based on earlier calls. For participants who previously set goals and identified PA resources to engage with, the counselor will assess progress, identify additional PA resources if needed, and work with the participants to set new, longer-term PA goals. If participants did not set goals or selected PA resources to try during calls 1 or 2, they will be invited to do so at this time.

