8.3 ADVERSE EVENTS AND SERIOUS ADVERSE EVENTS

8.3.1 DEFINITION OF ADVERSE EVENTS

This protocol uses the definition of adverse event from DHHS Office for Human Research Protections (OHRP): Any untoward or unfavorable medical occurrence in a human subject, including any abnormal sign (for example, abnormal physical exam or laboratory finding), symptom, or disease, temporally associated with the subject's participation in the research, whether or not considered related to the subject's participation in the research (modified from the definition of adverse events in the 1996 International Conference on Harmonization E-6 Guidelines for Good Clinical Practice).

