8.3.4 TIME PERIOD AND FREQUENCY FOR EVENT ASSESSMENT AND FOLLOW-UP

The occurrence of an AE or serious adverse event (SAE) may come to the attention of study team members during study visits. All AEs, not otherwise precluded per the protocol, will be captured on the Adverse Event Form. Information to be collected includes event description, time of onset, PI or co-investigator's assessment of severity, relationship to study procedures (assessed only by those with the training and authority to make a diagnosis), and time of resolution/stabilization of the event. All AEs occurring while on study will be documented appropriately regardless of relationship. All AEs will be followed to adequate resolution.

Any medical or psychiatric condition that is present at the time that the participant is screened will be considered as baseline and not reported as an AE. However, if the study participant's condition deteriorates at any time during the study, it will be recorded as an AE.

Changes in the severity of an AE will be documented to allow an assessment of the duration of the event at each level of severity to be performed. Documentation of onset and duration of each episode will be maintained for AEs characterized as intermittent.

The Project Coordinator will record events with start dates occurring any time after informed consent is obtained until 7 (for non-serious AEs) or 30 days (for SAEs) after the last day of study participation. Participants are identified in the EMR as a study participant and for each AE/SAE occurrence, research team members will receive an alert through EMR. AEs or SAEs may also be reported to study PA coach during the course of intervention visits. Events will be followed for outcome information until resolution or stabilization.

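### Section 8.2 words adverse-event capture more narrowly than Sections 8.3.1 and 8.3.4, and no adverse-event question is specified, so minor exercise harms may be missed

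*Combined protocol and SAP*

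**What the plan says.** **Scope.** Section 8.2 (Safety Assessments) sends events to the Adverse Events form on the condition "If a study team member learns of any adverse events (AEs) that occur in the course of participants' home exercise". Section 8.3.1 defines an AE as any untoward occurrence "whether or not considered related to the subject's participation in the research". Section 8.3.4 states: "All AEs occurring while on study will be documented appropriately regardless of relationship".

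**Setting of the activity.** Phase 3 in Section 6.1 links participants to resources "which include tools to facilitate individual PA, as well as group-based classes". It mentions walking groups and senior-centre classes.

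**Channels.** Under Section 8.3.4, events "may come to the attention of study team members during study visits", and "AEs or SAEs may also be reported to study PA coach during the course of intervention visits". The same section describes an EMR alert to the research team. In Section 1.3 the "Adverse Event Reporting" row is marked at Visits 1 to 6 and in the follow-up email column.

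**Emails.** Section 6.1 says that "the counselor will ask participants to opt-in (or opt-out) to receive follow-up emails after the 2-week check in call". Three are sent, about three weeks apart, before the 3-month call. Their stated content is the participant's activity goals.

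**Harms expected.** Section 2.2.1 names soreness, joint pain and injury as risks of the exercise programs.

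**The concern.** There are two linked problems.

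First, Section 8.2 and Section 8.3.4 describe different sets of events. A fall in a community class to which the counselor referred the participant is outside the wording of Section 8.2 and inside Section 8.3.4. Staff working from one section could record differently from staff working from the other.

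Second, the schedule says when AEs are reported but not how they are elicited. If nobody is required to ask, the count depends on who volunteers information and on what reaches the EMR. The harms that Section 2.2.1 names are the kind that people often manage themselves.

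At stake is how a low count would be read. Participants are 65 or older with painful osteoarthritis and at least one other chronic condition. The study is classed as minimal risk, and no monitoring board is planned unless the funder advises one (Sections 2.2.3 and 10.1.6). These records would be the main safety information carried into the larger trial that Section 8.1 anticipates. Without a fixed question, few events could mean few harms or few reports.

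**Working it through.** The protocol states no AE rate, capture rate or safety sample size, so there is no figure of its own to reproduce. The check is a comparison of sections plus calendar arithmetic.

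**1. Is an AE question specified anywhere?**
- Section 6.1 sets out the call content: stage of change, benefits of activity, preferences and resources, goals, setbacks, progress and barriers. It lists no AE item.
- Section 8.1 lists the accelerometer, WOMAC, fatigue, sleep, IPAQ, participant characteristics, feasibility and acceptability. It lists no AE item.
- Section 8.3.4 names three channels: staff noticing, reports to the coach, and the EMR alert. None is a question put to every participant.
- Section 8.3.4 nevertheless asks for onset, resolution, duration at each severity level, and every episode of an intermittent event. Spontaneous reports are a weak source for that detail on soreness or joint pain.

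**2. How long is the longest interval between scheduled calls?**
Inputs from Section 1.3: Visit 4 is 2 weeks, Visit 5 is 3 months and Visit 6 is 4 months after Visit 3.
- Calendar months (365.25/12/7 = 4.348 weeks): Visit 5 falls at 3 × 4.348 = 13.04 weeks. The gap is 13.04 − 2 = 11.04 weeks. Visit 3 to Visit 6 is 4 × 4.348 = 17.39 weeks. Share: 11.04/17.39 = 63.5%.
- Four-week months: the gap is 12 − 2 = 10 weeks out of 16, or 62.5%.

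**3. What do the emails change?**
Counting three weeks at a time from Visit 4, they fall at about weeks 5, 8 and 11. For those who opt in, scheduled contacts are then at most about 3 weeks apart. For those who opt out, the interval stays at about 11 weeks. The protocol does not estimate how many will opt out.

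**4. What would incomplete capture do to a reassuring result?**
This is an illustration on assumed capture probabilities, not an estimate for this trial. If no participant of 60 has a given event recorded, the one-sided 95% upper bound on the recorded rate is 1 − 0.05^(1/60) = 4.9%. Dividing by an assumed capture probability gives the bound on the true rate:

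| Assumed capture | Upper bound |
|---|---|
| 100% | 4.9% |
| 75% | 6.5% |
| 50% | 9.7% |
| 25% | 19.5% |

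The same zero is compatible with quite different true rates, and nothing in the protocol says which row applies.

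**The case against.** The strongest reply is that Section 8.2 is a lead-in. It points forward to the procedures in Section 8.3, where the definition and the documentation rule are unrestricted. That stands. A reader might infer that Section 8.2 excludes events outside the home, but it is narrower than Section 8.3.4 without expressly excluding anything. The fall in a community class is recordable under Section 8.3.4. The defect is inconsistent wording.

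Capture is also not confined to scheduled calls. EMR alerts run throughout, Section 6.1 lets participants contact the counselor with questions about resources, and Section 8.1 adds staff calls around accelerometer wear, whose timing relative to the gap is unclear. Section 8.3.4 accepts any event that starts after consent and records its onset, so an event in week 7 can still be entered at Visit 5. This also stands: 11 weeks measures the spacing of calls, not lost observation. It does not supply a question that would bring out the week-7 event at Visit 5.

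Detailed call scripts, an AE form and a Manual of Procedures are mentioned but are not part of the documents. One can say that the protocol specifies no question. One cannot say that participants are never asked.

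Finally, there is no safety objective (Section 3), the analyses are descriptive (Section 9.1), and the minimal-risk classification was made in advance. That limits the consequence but does not remove the value of an interpretable harm count.

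**Conclusion.** The point holds in a limited form, with moderate confidence. Sections 8.2 and 8.3.4 differ in scope and must be reconciled. Because only spontaneous reports and EMR alerts are described, soreness, joint pain and minor injury that do not reach the EMR may be missed. The risk is plausibly greatest in the roughly 11 weeks between Visits 4 and 5 for participants who decline the emails. This rests on the assumption that self-managed complaints often generate no EMR entry, and on the scripts and manual containing no AE question.

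The documents do not support three stronger readings. A reader might infer that harms are certain to be under-counted, or by a particular number, but no event or capture rate is given and the size cannot be computed. A reader might infer that most of the loss falls in the 11-week gap, but events there can be recorded later by onset date. A reader might also take the gap to be when new activity begins. Section 6.1 instead sets the first goals for the two weeks before the check-in call, which already asks about connection with programs; only participants not ready at the first call would start later.

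**What to change.** 1. Remove the home-exercise wording from Section 8.2 so that it covers any event in any setting, as Section 8.3.4 does.
2. Add one fixed AE question set to the existing calls at Visits 3, 4, 5 and 6. It should cover the period since the last contact: new or worse pain, injury, fall, emergency visit or hospital stay, with dates. Enter a yes/no answer in REDCap for every participant at each call, so that a recorded no can be told apart from a question not asked.
3. Add a reply prompt about events to the follow-up emails, or remove their mark from the AE row in Section 1.3.
4. Report solicited and spontaneous events separately, so that asking does not look like a rise in harm.

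If the scripts or manual already contain such a question, citing it in Section 8.3.4 would meet much of item 2. The cost is protocol wording, one REDCap form and about 1 to 2 minutes on calls that already take place. The downside is more minor events to record and review.
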